## 2 BACKGROUND AND RATIONALE

Figure 1. L-arginine, NOS and ADMA metabolism

[figure not shown]
**Obesity is one of the most significant comorbidities associated with poor asthma control, high exacerbation rates and increased frequency of healthcare utilization.** Considering that in the United States roughly

30% of the population is obese, understanding how it adversely affects asthma is a significant research and public health priority. Increasing body mass index (BMI) inflicts a mechanical load to the respiratory system which predictably increases the frequency and severity of respiratory complaints, particularly shortness of breath, in obese asthmatics (16). In addition, obesity may cause or be the result of dysfunction beyond the mechanical load with impacts of the pathobiology of asthma and/or response to treatment. In different cluster analyses of asthma populations, obese patients with asthma have been identified as a “clinical phenotype” characterized by late onset asthma, reduced atopy, and disproportionate symptoms resulting in high rates of healthcare and medication use. These patients have relatively well preserved lung function and low levels of traditional Th-2 cytokine related airway inflammation, including sputum eosinophils and exhaled nitric oxide (eNO) (17-19). **Obese, late onset asthmatics are a unique phenotype.** Among obese subjects, eNO is relatively lower among those with a greater BMI and later asthma onset vs. those with earlier, childhood onset (20). This observation suggests that the interaction of obesity with late onset age of asthma is what determines lower eNO levels in the obese asthma phenotype. This concept is further supported by the fact that the inverse association between increasing BMI and eNO is only significant among those with late onset asthma (> 12 years) (2). Although higher levels of eNO are thought to be part of the pathophysiology of asthma, a causal role in asthma has not been established. In fact, inhibition of NOS may not benefit humans whereas NO inhalation has been reported to prevent bronchial hyperresponsiveness (21-24). NO contributes to airway physiology by playing a role in airway smooth muscle and vascular relaxation. Reductions in eNO in obese patients with asthma, may be indicative of a detrimental derangement of airway NO metabolism (25).

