#### **4.2 Secondary Outcomes**

To determine whether, compared to baseline, treatment with NOx + CLA can:

- a) Increases eNO levels
- b) Quantify the concentrations of nitrate/nitrite in plasma and urine, free cLA in plasma, and NO2-cLA in BALF, plasma, and urine
- c) Reduce airway oxidation and inflammation
  - a. Western and RTPCR NF-κB and Nrf2 pathways in airway macrophages and PBMCs
  - b. Airway leptin and adiponectin
  - c. Proportion of airway TH-17 cells/responses

- d) Airway XO activity determined in endobronchial biopsies
- e) Measurement of  $^{15}\text{NO}_2\text{-cLA}$  and endogenous  $^{14}\text{NO}_2\text{-cLA}$  in urine, plasma and BAL
- f) Decrease production of anion superoxide in fresh airway epithelial cells;
- g) Mitochondrial ROS production and bioenergetics in fresh and cultured airway epithelial cells. As a potential source for airway / epithelial oxidative stress

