### 4.3 Exploratory Outcomes

To determine whether treatment with NOx + CLA can:

- a) Explore pre and post bronchoscopy changes in airway microbiome.
- b) Compare outcomes obtained at baseline between healthy controls participating in EFADA and obese asthmatics with metabolic syndrome

[figure not shown]

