## 5 RESEARCH DESIGN AND METHODS

### 5.1 Study Design

This is an open-label, single center, proof of concept pilot study in obese asthmatics.

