### **7.2 Inclusion Criteria**

- 1) Adequate completion of informed consent process with written documentation
- 2) Male and female patients, ≥ 18 - 65 yrs old
- 3) Diagnosis of asthma: based on previous physician diagnosis and either baseline pre-bronchodilator FEV1 50% or greater predicted with a 12% or greater

bronchodilator response to 4 puffs of albuterol or PC20 methacholine (16 mg) if no BD response. If the subject is not currently on an ICS or ICS-LABA combination, PC20 should be < 8 mg, if no BD response. Spirometry results within the prior 24 months located in the subject's medical records can be used to determine eligibility, if available.

- 4) From all racial/ethnic backgrounds with a diagnosis of asthma for  $\geq 6$  months;
- 5) Smoking history  $\leq 10$  pack years and no smoking in the last year;
- 6) BMI  $\geq 30$
- 7) If subject is on ICS or ICS/LABA therapy- 30 days on a stable dose (up to 1,000 mcg daily fluticasone equivalent)

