## **8.3 Efficacy Analyses**

Primary analysis: The primary analysis will test whether there is a significant difference in exhaled NO and measures of airway oxidative stress (superoxide production, XO activity in biopsies) before and after taking either of the intervention arms. This analysis will utilize an approach of comparing average values pre and post intervention, using matched paired comparisons.

Matched analysis are very efficient in controlling for confounders, as the analysis uses the same individual as case and control under different treatment conditions. Secondary outcomes will be tested following the same scheme of pre and post matched comparisons. To determine the relevance of measured variables, these will be compared to results from healthy controls undergoing bronchoscopy as part of the Electrophilic Fatty Acid Derivatives in Asthma (EFADA) study (IRB#: PRO11010186). This analysis will allow cross sectional comparisons and determine, for example, how obesity influences some of the baseline study variables.

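### The comparison with EFADA healthy controls in 8.3 cannot determine how obesity influences baseline variables, because the planned difference mixes obesity with asthma and its treatment

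*Combined protocol and SAP*

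**What the plan says.** After describing the paired pre/post analysis, section 8.3 adds a comparison with people outside the trial. To judge the relevance of the measured variables, "these will be compared to results from healthy controls undergoing bronchoscopy" in the EFADA study. It then states what this will show: "This analysis will allow cross sectional comparisons and determine, for example, how obesity influences some of the baseline study variables".

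Section 4.3(b) lists the comparison among the exploratory outcomes: "Compare outcomes obtained at baseline between healthy controls participating in EFADA and obese asthmatics with metabolic syndrome".

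On the trial side, section 5.1 describes a "proof of concept pilot study in obese asthmatics". Section 7.2 requires both an asthma diagnosis and a BMI of at least 30. Controller treatment is allowed but not required: "If subject is on ICS or ICS/LABA therapy- 30 days on a stable dose".

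On the control side, the documents say only that these people are healthy, underwent bronchoscopy and took part in EFADA. Their number, BMI and eligibility rules are not given. No covariate adjustment, matching rule or regression model is stated for the comparison.

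**The concern.** A contrast between two groups can be credited to one factor only if the groups are otherwise alike or the other differences are handled in the analysis. Here the groups differ in asthma by definition, in asthma treatment for some participants, and in obesity to an unknown degree. Section 8.3 nevertheless names obesity as the factor whose influence will be determined.

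The protocol's own background shows why this matters for the variables being measured. Exhaled NO (eNO) is an outcome (4.2(a), "Increases eNO levels"). Section 2 says: "Although higher levels of eNO are thought to be part of the pathophysiology of asthma, a causal role in asthma has not been established". It also reports that "the inverse association between increasing BMI and eNO is only significant among those with late onset asthma". An asthma component and an obesity component could therefore pull eNO in opposite directions and partly cancel. Section 2 likewise explains low L-arginine/ADMA ratios in obese asthmatics by two sources together: reduced L-arginine in asthma, and raised ADMA linked to obesity or metabolic syndrome. L-arginine is not a listed endpoint, but plasma ADMA is (Specific Aim 2).

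If 8.3 is followed as written, a published difference could be labelled an effect of obesity when it also contains asthma and its treatment. The abstract offers the results as a basis for understanding obese asthma and for designing later trials, so the label matters even for an exploratory result.

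**Working it through.** The plan gives no figure for this comparison, so there is none to reproduce. The question is what the planned difference estimates.

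**Inputs from the documents**
- Trial group: all obese, all asthmatic (5.1, 7.2); ICS or ICS/LABA allowed (7.2).
- Control group: all healthy; BMI not stated (8.3, 4.3(b)).
- Method: an unadjusted cross-sectional comparison, since 8.3 states no other. Its pre/post pairing cannot apply to different people.

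**Step 1: what the difference contains.** Code obesity as yes/no. Let o be the obesity effect, a the net effect of asthma and its treatment, p the fraction of controls who are obese, and m the mean in lean healthy people. Assume for now that the effects add.
- Trial mean = m + o + a
- Control mean = m + p × o
- Planned difference = a + (1 − p) × o
- Error if this is read as o = a − p × o

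The difference equals o only if a = p × o. With lean controls (p = 0) that requires a = 0, meaning that asthma and its treatment have no net effect. If every control were obese (p = 1), the difference would be a alone, with no obesity component.

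**Step 2: without additivity.** Let the obesity effect be oA in asthmatics and oH in healthy people. The difference becomes a + oA − p × oH, which in general is neither oA nor oH.

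**Step 3: rank check, yes/no coding, lean controls.** For intercept, obesity, asthma and ICS, the design has rank 2 of 4 if all participants use ICS. It has rank 3 of 4 if some do not. In the second case ICS separates, but obesity and asthma remain inseparable.

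**Step 4: illustration of the algebra.** The values o = −0.5 SD, a from −0.5 to +0.5 SD, and p are all assumed; the documents give none of them.

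| p | a = −0.5 | a = 0 | a = +0.5 |
|---|---|---|---|
| 0 | −1.00 | −0.50 | 0.00 |
| 0.25 | −0.875 | −0.375 | +0.125 |
| 0.5 | −0.75 | −0.25 | +0.25 |

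For example, with p = 0.25 and a = +0.5: 0.5 + 0.75 × (−0.5) = +0.125. The table shows only that the difference can fall on either side of o. It does not estimate the error in this trial.

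**Step 5: comparability of the groups.** Section 7.3 excludes current statin users because statins lower ADMA, and users of chlorhexidine mouthwash because it lowers NO. The documents do not say whether the EFADA controls met the same restrictions. A difference in ADMA or eNO could reflect this as well.

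**The case against.** The strongest reply is that the comparison has a sound purpose and the disputed words are a small part of it. Section 8.3 introduces it as a way to judge the relevance of the measured variables, which is an ordinary use of a healthy reference group. The obesity clause is given as an example and covers only some variables. No hypothesis, primary outcome or sample size depends on it. This stands, and it limits the weight of the point. It does not make the example valid: the design cannot support that inference.

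A second reply is that BMI varies among participants. Entry is at BMI 30 or more with no upper limit, and Visit 1 records weight and height. With continuous BMI, a slope among the asthmatics could be estimated even with a BMI-by-asthma term. That is correct. A reader might infer from the rank check that the trial data can carry no information about adiposity; the documents do not support that, since the rank result depends on yes/no coding. But no BMI model is planned, and a slope above BMI 30 is an association within obesity, not obese against non-obese.

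A third reply concerns the controls. A reader might infer that they were not restricted on statins or mouthwash. The documents are silent, EFADA has its own protocol, and silence here does not show that restrictions were absent.

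Finally, a reader might see a contradiction between 4.3(b), which names metabolic syndrome, and 7.2, which does not require it. Waist circumference and vital signs at Visit 1 and the metabolic blood work at Visit 3 allow 4.3(b) to be read as a subgroup derived from collected data. What remains is that 8.3 does not say which population it uses.

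**Conclusion.** The point holds. As planned, the difference between obese asthmatics and EFADA healthy controls combines obesity with asthma and its treatment, and the statement in 8.3 about the influence of obesity does not follow from it. This conclusion needs no assumed number. It rests on the entry criteria, on the comparators being healthy, and on the absence of any planned adjustment, matching, BMI model or non-obese asthma group.

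The size and direction of the error cannot be given. A reader might infer from the illustration that the reported obesity effect would be doubled, cancelled or reversed. Those outcomes come from letting the assumed asthma-plus-treatment effect be as large as the assumed obesity effect, and no figure in the documents supports that range.

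The reach is limited to the exploratory baseline comparison in 4.3(b) and 8.3. The paired pre/post analyses do not use the controls and are unaffected. The wording should be corrected, but the point does not threaten the trial's main analysis.

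**What to change.** 1. In 8.3, replace the sentence on obesity with, for example: *This comparison describes how baseline values in obese asthmatics differ from those in a healthy reference group; it does not estimate the effect of obesity.*
2. Report the controls' BMI, and their statin and chlorhexidine mouthwash status, where EFADA recorded them. Where it did not, say so.
3. Claim an obesity-versus-non-obesity effect in asthmatics only if comparable non-obese asthmatics are used as the comparator. Label any BMI slope among the trial participants as a within-obese association.
4. State in 8.3 whether the comparison uses all participants or the metabolic syndrome subgroup named in 4.3(b). The documents do not favour either.

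Items 1, 3 and 4 are wording. Item 2 adds a few descriptive rows and depends on what EFADA holds. No new participants or procedures are needed, and the paired analyses do not change. The downside is a weaker claim: the trial would say nothing about obesity as such unless comparable non-obese asthmatics become available.

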## **8.4 Safety Analyses**

Due to the relatively short duration of this POC, we do not expect to see a large number of exacerbations during the treatment period. However, the rate of exacerbations will be monitored and reported to the DSMB at their regularly scheduled meetings to ensure the safety

of study participants. In addition, as CLA and NOx have not been used in combination for the treatment of asthma, therefore as a POC we will monitor lung function and bronchial hyperresponsiveness.

## **8.5 Handling Missing Data**

Because of the possibility of drop-outs and other missed visits, there will be some missing data. The statistical models and analyses that are planned for the primary and secondary outcomes assume that the data are missing-at-random (MAR). Because likelihood-based methods will be applied, MAR data still yield valid estimates. Although not expected, if it appears that the MAR assumption is not reasonable, then non-ignorable statistical analyses, such as shared parameter modeling will be applied.

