- The research coordinator will contact the subject 24-48 hours prior to Visit 3 in order to verify the medication withhold and readiness for the bronchoscopy procedure.
- Pt arrives to CTRC – MUH after an 8 hour fast
- Urine pregnancy test in females of child-bearing potential (i.e. women who are not at least 1 year post-menopausal or who have not undergone a surgical sterilization procedure).
- A physical exam will be completed
- The subject must have used less than 16 puffs of albuterol in the last 48 hours in order to proceed with bronchoscopy procedures
- Pre – bronchoscopy spirometry (pre- and post-bronchodilator) (safety assessment)
- Asthma Control Questionnaire (ACQ)& pre-bronchoscopy safety checklist
- Tongue scrape x microbiome
- Bronchoscopy for a) brushings , b) BAL, c) endobronchial biopsies; d) microbiome
- Blood work for metabolic syndrome ( fasting blood glucose, insulin levels, serum creatinine) lipid profile (HDL, triglycerides, total cholesterol, LDL and VLDL), CBC with differential, and Hgb A1C.

- Plasma collection
- Urine collection X Prostaglandin D2 (PGD2) metabolites and isoprostanes
- Exhaled NO (No food, drink (other than water), or strenuous exercise 1 hour prior to visit)
- Stool x microbiome
- Post bronchoscopy spirometry
- Dispense study drug supply- 4 week supply
- Distribute study Diary Card and review instructions

Phone call visit T1 (2 weeks after Visit 3)

- Review diaries & compliance
- ACQ
- Review any concerns and health care utilization

Visit 4 (4 weeks after Visit 3)

- Short Physical Exam
- Review of diaries and compliance
- Niox Mino (No food, drink (other than water), or strenuous exercise 1 hour prior to visit)
- Pre and Post spirometry
- ACQ & ACT
- Dispense 4 week supply of study drug

Visit 4A (if necessary)

If it is determined by the study coordinator at Visit 4 that the subject has not taken at least 75% of the study drug, the coordinator will provide a 1 week supply of the study drug and ask the subject to return to the Asthma Institute for a compliance check (visit 4A). If the subject is not compliant at Visit 4A, the subject will be withdrawn from the study. If the subject has improved compliance after 1 week, the remaining 3 week supply of the study drug will be dispensed.

Phone call visit T2 (6 weeks after Visit 3)

- Review diaries & compliance
- ACQ
- Review any concerns and health care utilization

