#### Visit 6 (End of study- 24 hours to 1 week after visit 5)

- Pt arrives to CTRC – MUH after an 8 hour fast
- Pre – bronchoscopy spirometry (pre- and post-bronchodilator) (safety assessment)
- Pre-bronchoscopy questionnaires: ACQ, ACT, and pre-bronchoscopy safety checklist
- A brief physical exam will be completed
- Urine pregnancy test in females of child-bearing potential (i.e. women who are not at least 1 year post-menopausal or who have not undergone a surgical sterilization procedure).
- Tongue scrape x microbiome
- Bronchoscopy for a) brushings , b) BAL, c) endobronchial biopsies; d) microbiome
- Blood x plasma collection Urine x PGD2 metabolites and isoprostanes
- Exhaled NO (No food, drink (other than water), or strenuous exercise 1 hour prior to visit)
- Stool x microbiome
- Post bronchoscopy spirometry

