### End of Study Visit

If a subject is withdrawn from study participation, an End of Study Visit will be scheduled. This visit will take place at the Asthma Institute and will consist of the following procedures:

- Physical Exam
- Spirometry
- ACQ
- Review of diaries

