### **Bronchoscopy**

Risk from bronchoscopy are hemoptysis, epistaxis, and local discomfort, fever and a sore throat. Sedation will be given as part of the bronchoscopy and the medications used for this can cause hypotension, lightheadedness or dizziness; these side effects are somewhat common but very short in duration. Appropriate monitoring equipment and medications will be used to promptly identify and manage complications if they occur. Bronchoscopy may cause coughing and occasionally gagging. Fever or chills may occur, especially following a lavage. Chest pain from a collapse of a small segment of the lung (atelectasis) may occur. Some people experience temporary vomiting, soreness of the nose and throat Mild to moderate cough can be

observed for 24 hours after the procedure. The greatest risk of bronchoscopy is transient worsening of asthma. This rarely occurs in mild-moderate asthmatic subjects (<5%), but can occur in up to 25% of severe asthma subjects. Every precaution is taken to prevent this, including giving 40-60 mg of prednisone to severe asthmatics prior to discharge. The subject's asthma may worsen during or after the procedure. In those rare cases, we may ask them to spend the night in the Clinical Translational Research Center (CTRC). There has been only one death (worldwide) associated with a research bronchoscopy so this is very, very rare event. Overall, research bronchoscopy in adult asthmatics is a safe and well-tolerated procedure (49).  
Protection against Risk: First during the bronchoscopy, patients are placed on supplemental oxygen and monitored continuously with oxygen saturation monitor as well as electrocardiogram. Due to the potential of increased risk of complications with asthmatic subjects undergoing a bronchoscopy, subjects are pretreated with beta-agonists. The topical anesthesia and sedation dosages are monitored and limits set and adhered to closely. Research bronchoscopies will only be done on subjects with a post bronchodilator FEV1 predicted of ≥50%.

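### Section 8.5 claims validity under MAR from likelihood-based methods, but section 8.3 plans only paired pre/post comparisons and does not fix the eNO visits

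*Combined protocol and SAP*

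**What the plan says.** Section 8.5 expects some missing data, assumes it is missing at random for both primary and secondary outcomes, and gives this reason for not being troubled by it: "Because likelihood-based methods will be applied, MAR data still yield valid estimates." If MAR looks unreasonable, it turns to non-ignorable methods and gives shared-parameter modelling as the example.

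Section 8.3 describes the primary analysis of eNO, superoxide production and XO activity: "This analysis will utilize an approach of comparing average values pre and post intervention, using matched paired comparisons." For the rest: "Secondary outcomes will be tested following the same scheme of pre and post matched comparisons." It names no likelihood, covariance structure or visit structure.

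Section 6 schedules eNO at six visits: 1, 2 and 3 before treatment, 4 at mid-treatment, and 5 and 6 at the end. Visit 3 is labelled Week 0 and Visit 6 End of study. Under Visit 4A, a participant who took less than 75% of study drug gets a one-week check, and then: "If the subject is not compliant at Visit 4A, the subject will be withdrawn from the study." The End of Study Visit for withdrawn participants lists physical examination, spirometry, ACQ and diary review. It lists neither eNO nor bronchoscopy.

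**The concern.** The validity claim in 8.5 belongs to a class of analysis that 8.3 does not specify. An analyst who reads 8.3 literally would run a paired test on participants with both values. That analysis discards every incomplete pair, including Visit 4 readings that could help explain who was lost. The report could then cite 8.5 for a protection the analysis did not have.

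The undefined pre and post values for eNO add a second freedom. Two analysts could produce different primary eNO results from the same complete data, and nothing stops the choice being made after the data are seen.

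**Working it through.** **Inputs.** The plan gives no eNO variance, dropout rate or dropout mechanism, so there is no figure on this point to reproduce. The sample size of 12 comes from section 8.1, where it is sized on methacholine PC20. It reproduces as a two-group total: 2(1.960 + 1.282)²(1.9/3.8)² = 5.25, so 6 per group and 12 in all. Whether that form suits a paired design is a separate matter. Everything else below is assumed: within-person visit SD 1, intraclass correlation 0.6, 20% lost after Visit 4, and SD τ of individual treatment effects of 0, 0.5 or 1.

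**1. Readings used.**

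| Visit | Timing | eNO | Superoxide, XO | Same-day procedure |
|---|---|---|---|---|
| 1 | before | yes | no | screening |
| 2 | before | yes | no | methacholine |
| 3 | Week 0 | yes | yes | bronchoscopy |
| 4 | week 4 | yes | no | spirometry |
| 5 | week 8 | yes | no | methacholine |
| 6 | end of study | yes | yes | bronchoscopy |

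A single Visit 3/Visit 6 pair uses two of the six eNO readings and leaves Visits 1, 2, 4 and 5 unused. A participant withdrawn at Visit 4A contributes four readings to a likelihood model and none to that pair.

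**2. Why complete pairs lack the stated property.** Let D4 be Visit 4 minus the mean of Visits 1 to 3, and D6 be Visit 6 minus Visit 3. With independent visit errors, the covariance of D4 and D6 is 1/3 + τ² and the variance of D4 is 4/3 + τ². The regression slope of D6 on D4 is therefore:

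- τ = 0: (1/3)/(4/3) = 0.25
- τ = 1: (4/3)/(7/3) = 0.57

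If participants with a poor D4 are lost more often, mean D4 among those kept is too high. The complete-pair mean is then too high by the slope times that excess. The slope is positive even when everyone has the same treatment effect, because Visit 3 enters both differences.

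**3. Size, by simulation.** Loss is logistic in D4, with slope 1 or 2 per SD. For a true change of 0.50, complete-pair within-person averages (Visits 5 and 6 minus Visits 1 to 3) give 0.55 to 0.73. The bias is 0.05 to 0.23 visit SD, or 0.18 to 0.55 SE; a second set of runs gave 0.14 to 0.58 SE. With no true change, two-sided type I error is 5.0 to 7.5% against 5%, or 5.1 to 6.2% for a Visit 3/Visit 6 pair.

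A mixed model on all visits, for the same contrast, gives 0.47 to 0.52, within 0.10 SE of the truth. If loss depends instead on the unobserved individual effect (τ = 1), complete pairs give 0.67 to 0.76 and the model 0.57 to 0.62.

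**4. Precision from averaging.** This is the SE with two readings per side relative to one:

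- Independent errors, common effect: √[(1/2 + 1/2)/2] = 0.707, 29% lower.
- Independent errors, τ = 1: √[(1/2 + 1/2 + 1)/3] = 0.816, 18% lower.
- Same-side error correlation 0.5, so each mean has variance (1 + 0.5)/2 = 0.75: √(1.5/2) = 0.866, 13% lower; with τ = 1, √(2.5/3) = 0.913, 9% lower.

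The correlated case matters because Visits 5 and 6 may be only 24 hours apart.

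**5. Balance.** Suppose methacholine days or bronchoscopy days shift eNO. Visits 5 and 6 minus Visits 1 to 3 keeps 1/2 − 1/3 = 1/6 of each shift. Visits 5 and 6 minus Visits 2 and 3 keeps 1/2 − 1/2 = 0.

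**The case against.** Several defences stand in part.

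A reader might infer that 8.3 and 8.5 contradict each other. The documents do not support that. A matched comparison can be fitted by likelihood, and with complete pairs a two-time-point mixed model gives the same estimate as the paired test. Nor is the plan without any model: the shared-parameter fallback addresses loss that depends on unobserved values, where the mixed model stays biased. What remains is that the main analysis is never tied to a likelihood.

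A reader might also infer that the eNO pair is wide open. The Week 0 and End of study labels point to Visits 3 and 6, which are also the only visits available for superoxide and XO in the same primary analysis. The gap is that the text does not say so, and that this choice sets aside four scheduled readings.

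The loss mechanism is assumed. The documented withdrawal trigger is adherence, not eNO. Complete pairs are unbiased if loss is unrelated to eNO, and about unbiased in simulation if it depends on the Visit 4 level alone.

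For the bronchoscopy endpoints, section 9.1.1 says "Research bronchoscopies will only be done on subjects with a post bronchodilator" FEV1 of at least 50% predicted, so a second value could be missing because of that day's FEV1. But participants have already met this requirement at Visit 3, and the documents give no failure rate. Substantial informative loss is therefore not shown.

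Finally, this is an open-label pilot whose eNO endpoint section 8.1 admits it cannot power. That limits the consequence, but it does not supply the missing link between 8.3 and 8.5.

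**Conclusion.** The point holds as an unsupported validity claim together with an under-specified eNO comparison. Run as ordinary complete pairs, the plan does not have the MAR property it states for its primary and secondary outcomes, and the scheduled readings that could support the claim for eNO go unused.

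The effect is modest and conditional: a bias of about 0.2 to 0.6 SE and a two-sided type I error of about 5.0 to 7.5% against 5%. Both rest on 12 participants, 20% loss and dependence on observed Visit 4 change; only the 12 is in the documents. A large rise in false positives should not be inferred. The one-tail rate for an increase (3.4 to 6.8% against 2.5%) looks worse, but section 8.1, the only place that states sidedness, specifies a two-sided test.

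The open choice of eNO visits needs no dropout assumption and matters even with complete data.

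**What to change.** **eNO, in section 8.3.** Analyse all readings from every treated participant, Visit 4 included, with a likelihood-based repeated-measures model: visit as a factor, a stated covariance structure and small-sample degrees of freedom. Name one primary contrast: mean of Visits 5 and 6 minus mean of Visits 2 and 3, so that methacholine and bronchoscopy days match. If the model does not converge, use the paired comparison of the same within-person averages and say that it applies to completers.

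**Superoxide and XO activity.** These exist only at Visits 3 and 6. Replace the MAR sentence with a statement that complete pairs are analysed and results apply to completers. Report the number of missing second bronchoscopies with reasons.

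A shift-type sensitivity analysis, or a model including the Visit 6 FEV1, is optional.

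**Cost.** No new data or visits; wording, slightly more analysis and a working covariance assumption. In simulation (contrast against Visits 1 to 3, fixed 11 degrees of freedom), the model was somewhat conservative. With complete data its coverage was 96 to 97%. Power fell by 2 to 7 points, for example from 0.411 to about 0.34 at τ = 0 and from 0.229 to about 0.21 at τ = 1. With 20% loss and no true change, it declared an increase in 0.7 to 2.5% of runs against a nominal 2.5%. The small-sample correction recommended here was not itself simulated. The model gives no protection if loss depends on unobserved response, or on adherence beyond what observed eNO explains.
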